5 TRIAL OBJECTIVES

5.1 Primary Objective

The primary objective is to determine the efficacy of the neuroprotectant, NA-1, in reducing global disability in subjects with major AIS with a small established infarct core and with good collateral circulation selected for endovascular revascularization.

5.2 Secondary Objectives

The secondary objectives are to determine the efficacy of NA-1 in:

- Reducing functional dependence
- Improving neurological outcome
- Improving activities of daily living
- Reducing mortality rate

5.3 Tertiary Objectives

The tertiary objectives are to determine the efficacy of NA-1 in:

- Improving health-related quality of life.
- Decreasing infarct volume at follow-up imaging
- Improving cognitive function

5.4 Leading Safety Objectives

The leading safety objectives are to determine the effect of administering a dose of 2.6 mg/kg (up to a maximum dose of 270 mg) intravenous infusion of NA-1 to subject with acute stroke who are selected for endovascular revascularization on SAEs and 90-day mortality.

6 TRIAL DESIGN

This is a Phase 3 randomized, multicentre, blinded, placebo-controlled, parallel group, single-dose design. Subjects harboring an acute stroke and who are selected for endovascular revascularization in accordance with local institutional practices and who harbor a small established infarct core and with good collateral circulation will be given a single, 2.6 mg/kg (up to a maximum dose of 270 mg) intravenous dose of NA-1 or placebo as soon as they are deemed to have met the enrollment criteria and with the intention of starting administration within 30 minutes of randomization.

A total of 1120 subjects aged 18 years and older will be enrolled into the study. All subjects will be followed for 90 days (or until death if prior to 90 days). Further details on the study procedures can be found in [Table 2-1: Schedule of Assessments](#). The end of study is defined as the date that the last enrolled subject has completed their Day 90 visit.

6.1 Outcomes

6.1.1 Primary Efficacy Outcome

The primary efficacy outcome variable for the pivotal assessment of efficacy for regulatory submission purposes is the overall proportion of subjects experiencing a favorable functional outcome 90 days post-randomization, defined as 0 to 2 on the mRS. These subjects are defined to be responders.

6.1.2 Secondary Efficacy Outcomes

The key secondary efficacy outcome is the shift of one or more categories to reduced functional dependence analyzed across the whole distribution of scores on the mRS at Day 90 or the last rating.

Other secondary outcomes include:

- 1) Proportion of subjects with good neurological outcome, as defined by a score of 0-2 on the NIHSS at Day 90 or the last rating.
- 2) Proportion of subjects with functional independence in activities of daily living, as defined by a score of ≥ 95 on the BI at Day 90 or the last rating.
- 3) A reduction in mortality rate, as defined by event rate (%) for mortality over the 90-day study period
- 4) Proportion of subjects with functional independence, as defined by a score of 0-1 on the mRS at Day 90 or the last rating.

6.1.3 Tertiary Outcomes

The following tertiary outcomes will be assessed descriptively:

- 1) Health-related quality of life, as measured by the EQ-5D-5L at Day 90 or the last rating.
- 2) Volume of stroke as measured by a) DWI and b) FLAIR at 24 Hour follow-up. If NCCT was done instead of MRI, Volume of stroke will be derived from hypodense areas.
- 3) Cognitive outcomes, as measured by the 15-item Boston Naming Test (BNT15), Sunnybrook Hemispatial Neglect Procedure (SNAP) and the Montreal Cognitive

Assessment (MoCA).

- 4) The proportion of subjects experiencing a favorable functional outcome 30 days post-randomization, defined as 0 to 2 on the mRS.

6.1.4 Safety Outcomes of Special Interest

The primary safety outcomes are the frequencies of SAEs and 90-day mortality.

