11.5.4 Mortality Rate

Mortality rates, as defined as the number of deaths observed divided by the number of subject observed over the 90 day study period between NA-1 and placebo control subjects, will be analyzed by the same logistic regression model as in the primary efficacy.

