11.9.2 Mortality

Event rate (%) for mortality over the 90-day study period between NA-1 and placebo control subjects will be compared by logistic regression. The logistic regression model will include factors for treatment group. All deaths will be provided in a listing.

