7.2.4 Mortality

Mortality will be assessed at Day 5 or discharge and at Days 30 and 90. Mortality rates, defined as the number of deaths observed divided by the number of subjects observed over the 90-day study period between NA-1 and placebo control subjects, will be analyzed by the same logistic regression model as in the primary efficacy. Subjects with missing outcomes will be treated as deaths for this analysis. The odds ratio associated with the treatment effect, adjusted for the stratification and covariates as described for the primary endpoint analysis, will be presented with a 95% confidence interval and the associated Wald test.

7.2.5 Proportion of subjects with Day 90 mRS ≤ 1

The Day 90 mRS score will be dichotomized at $mRS \leq 1$ (indicating freedom from disability) vs. $mRS > 1$ (indicating otherwise). The proportion of subjects with freedom from dependence/disability based on this dichotomy on Day 90 in NA-1 versus placebo control subjects will be compared using the same logistic regression model as in the primary efficacy analysis. Results will be summarized and tabulated.

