Secondary	Day-90 mRS	Ordinal (0-4,5+6)	ITT	mRS cumulative logits modeled as a function of treatment, baseline ASPECTS, occlusion location, age, sex, baseline NIHSS, alteplase*thromb_app, study site
	Day-90 NIHSS	Binary (≤ 2 vs. > 2)	ITT	logit(binary NIHSS) modeled as a function of treatment, baseline ASPECTS, occlusion location, age, sex, baseline NIHSS, alteplase*thromb_app, study site
	Day-90 Barthel	Binary (< 95 vs. ≥ 95)	ITT	logit(binary Barthel Index) modeled as a function of treatment, baseline ASPECTS, occlusion location, age, sex, baseline NIHSS, alteplase*thromb_app, study site
	Day-90 Mortality	Binary day-90 death status	ITT	logit(binary death status) modeled as a function of treatment, baseline ASPECT, occlusion location, age, sex, baseline NIHSS, alteplase*thromb_app, study site
	Day-90 mRS	mRS Binary (≤ 1 vs. > 1)	ITT	logit(binary mRS) modeled as a function of treatment, baseline ASPECTS, occlusion location, age, sex, baseline NIHSS, alteplase*thromb_app, study site
Tertiary	EQ-VAS	0-100	ITT	EQ-VAS modeled as functions of treatment, baseline ASPECTS, occlusion location, age, sex, baseline NIHSS, alteplase*thromb_app, study site
	Stroke volume	continuous	ITT	Stroke volume (or cubic root transformation of stroke volume) modeled as a function of treatment, baseline ASPECTS, occlusion location, age, sex, baseline NIHSS, alteplase*thromb_app, study site
	BNT15	0-15	ITT	BNT15 Score modeled as a function of treatment, baseline ASPECTS, occlusion location, age, sex, baseline NIHSS, alteplase*thromb_app, study site
	SNAP	0-100	ITT	Total SNAP Score modeled as a function of treatment, baseline ASPECTS, occlusion location, age, sex, baseline NIHSS, alteplase*thromb_app, study site
	MoCA	Binary (< 26 vs. ≥ 26)	ITT	logit(binary MoCA) modeled as a function of treatment, baseline ASPECTS, occlusion location, age, sex, baseline NIHSS, alteplase*thromb_app, study site
	Day-30 mRS	Binary (≤ 2 vs. > 2)	ITT	logit(binary mRS) modeled as a function of treatment, baseline ASPECTS, occlusion location, age, sex, baseline NIHSS, alteplase*thromb_app, study site
Exploratory	Day-90 mRS	Binary (≤ 2 vs. > 2)	ITT	Separate logistic regression models in which the logit(binary mRS) is modeled as a function of treatment only, by each of the subgroups to be considered in the Subgroup forest plots

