8.0 SAFETY ANALYSES

The safety population will consist of all subjects who received any dose of study drug. The main analyses will be frequency of SAEs and 90-day mortality. It is expected that the safety population and the ITT population will be near-identical.

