8.1 Adverse Events

Additional analyses will consider the frequency of AEs and discontinuations due to AEs.

AEs will be collected until Day 30 and SAEs will be collected until Day 90 or the final contact. AEs will be summarized by presenting, for each treatment group, the number and percentage of subjects having at least one AE, having an AE in each body system and preferred term, by severity and relatedness to study medication. The frequencies and incidences of AEs occurring in subjects in the drug and placebo control groups will be summarized within treatment group by the Medical Dictionary for Regulatory Activities (MedDRA) System Organ Class (SOC). The frequencies and incidences of discontinuations due to AEs occurring in subjects in the NA-1 and placebo control groups will be summarized within treatment group.

If a given subject had more than one AE mapped to the same preferred term, then that subject will be counted only once within that preferred term.

When reporting TEAEs by maximum severity, if a given subject had more than one AE mapped to the same preferred term, then that AE will be counted once according to the maximal level of severity (Severe, Moderate, Mild).

When reporting TEAEs by relationship to study treatment, if a given subject had more than one AE mapped to the same preferred term, then that AE will be counted once according to the highest level of relatedness (Related, Probably, Possibly, Unrelated).

The following summaries (tables) of AEs and TEAEs will be provided by number (percentage) of subjects for each treatment group:

- All TEAEs by MedDRA preferred term

- All TEAEs by MedDRA SOC and by preferred term
- TEAEs (with a start date 0-30 days) by MedDRA SOC and by preferred term
- Serious TEAEs (with start date 0-90 days) by MedDRA SOC and by preferred term
- All TEAEs resulting in death by MedDRA SOC and by preferred term
- Event rate (%) for Serious TEAEs over the 90-day study period between NA-1 and placebo control subjects will be compared by a logistic regression model similar to that of the primary analysis.
- All TEAEs occurring in at least 5% of subjects in either treatment arm, by MedDRA SOC and by preferred term.
- All TEAEs by maximum severity (Severe, Moderate, Mild) by MedDRA SOC and by preferred term. Missing severity grades will be assumed as 'severe'.

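### Protocol 11.9.2 names treatment as the only term in the safety comparison of 90-day mortality, SAP section 8 gives no mortality model, and no mortality estimate is designated as the lead one for harm

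*Protocol*

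**What the plan says.** Mortality at 90 days has a leading place in the safety plan. Protocol 6.1.4 states "The primary safety outcomes are the frequencies of SAEs and 90-day mortality", and SAP 8.0 repeats that "The main analyses will be frequency of SAEs and 90-day mortality".

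The analysis of deaths is described in two places with different purposes.

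- **As safety.** Protocol 11.9.2 compares the 90-day rates by logistic regression and adds: "The logistic regression model will include factors for treatment group". No other term is named. SAP section 8 specifies no mortality model; it plans tables of fatal events and a listing of deaths.
- **As a secondary efficacy outcome.** Under Protocol 11.5.4 mortality "will be analyzed by the same logistic regression model as in the primary efficacy". SAP 7.2.4 gives an odds ratio, "adjusted for the stratification and covariates as described for the primary endpoint analysis, will be presented with a 95% confidence interval", and a Wald test. SAP Table 2 lists the terms for the ITT population: "logit(binary death status) modeled as a function of treatment, baseline ASPECT, occlusion location, age, sex, baseline NIHSS, alteplase*thromb_app, study site". SAP 7.2.4 also sets the missing-data rule: "Subjects with missing outcomes will be treated as deaths for this analysis".

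The other primary safety outcome is handled differently. In SAP 8.1 the rate of serious treatment-emergent events "will be compared by a logistic regression model similar to that of the primary analysis", and the primary model is adjusted.

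**The concern.** Allocation is stratified on alteplase and declared device and minimized on age, sex, NIHSS, ASPECTS, occlusion location and site. The efficacy models use these variables. The one model written for deaths in a safety section names none of them, and no reason is given for treating deaths differently from serious events. When covariates predict death, a logistic model without them is the less powerful test.

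The report would also carry two mortality odds ratios that differ in population, covariates and missing-data rule. With no lead estimate named, the choice of which one speaks to harm could be made after unblinding.

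**Working it through.** **1. The plan's own figure.** The documents state no power for mortality. Their one power figure, for mRS 0-2, reproduces. With 538 per arm, 52% against 60.7%, and a two-look O'Brien-Fleming-type spending design at 600/1076 = 0.558 information, power is 81.8% (SAP 1.4: 81.7%). The one-sided boundaries are 0.0027 and 0.0241 (SAP 3.0: 0.003 and 0.024).

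**2. The two planned mortality analyses side by side.**

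| | Protocol 11.9.2 | SAP 7.2.4 and Table 2 |
|---|---|---|
| Population | Safety, by treatment received (SAP 2.2) | ITT, as randomized |
| Terms named | Treatment | Treatment, both strata, all six minimization variables |
| Missing outcome | Not stated | Counted as death |
| Role | Safety comparison | Fourth of five ordered secondary tests |

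**3. What adjustment adds.** Assumptions, not in the documents: placebo mortality 10%, 15% or 20%; marginal harm odds ratio 1.5; one prognostic score with AUC about 0.70 or 0.79. For 15%, the odds are 0.15/0.85 = 0.1765; times 1.5 is 0.2647; 0.2647/1.2647 = 20.9% under treatment. Simulated Wald tests, 560 per arm, two-sided 0.05, 3000 runs per cell, no missing data:

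| Placebo mortality | Treatment only | Adjusted, AUC 0.70 | Treatment only | Adjusted, AUC 0.79 |
|---|---|---|---|---|
| 10% | 58% | 61% | 60% | 67% |
| 15% | 73% | 76% | 73% | 81% |
| 20% | 82% | 86% | 83% | 89% |

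The gain is about 3 to 7 points. These runs did not use the minimization. A separate simulation with minimal-sufficient-balance allocation and a harm odds ratio of 1.6 gave a gain of 4 to 8 points. Null rejection there was 3.1-4.7% unadjusted and 3.7-6.0% adjusted (1000 runs each), so a little of that gain may reflect test size.

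**4. What counting missing as death removes.** With a missing fraction m unrelated to arm or outcome, each rate p becomes p(1 − m) + m. The documents supply two values for m: 1.3% (the earlier trial, SAP 5.1) and 4% (the planned inflation, SAP 1.4).

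- m = 1.3%: 15% becomes 16.1% and 20.9% becomes 22.0%; the odds ratio falls from 1.50 to 1.47.
- m = 4%: 15% becomes 18.4% and 20.9% becomes 24.1%; the odds ratio falls to 1.41.

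Power is Φ{[d√n − 1.96√(2p̄q̄)] / √(p₁q₁ + p₂q₂)}, with n = 560 per arm. With no missing data this is Φ[(1.403 − 1.064)/0.541] = 73.5%. At 1.3% it is 70.4%. At 4% it is Φ[(1.347 − 1.134)/0.577] = 64.4%.

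**5. Both effects together.** Same harm odds ratio, 2000 runs per cell (simulation error about 1 point), 4% missing; each range spans the weaker and stronger covariate setting:

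| Placebo mortality | Treatment only, observed deaths | Adjusted, observed deaths | Adjusted, missing = death |
|---|---|---|---|
| 10% | 56-58% | 61-63% | 49-50% |
| 15% | 72-73% | 76-81% | 67-72% |
| 20% | 82% | 85-89% | 79-83% |

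At 4% missing, the planned adjusted model falls below the treatment-only model in five of six cells. Against the adjusted observed-deaths model it loses about 5 to 12 points at 4% missing and about 2 to 5 at 1.3%.

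**6. Why site is a problem term for deaths.** SAP 6.5 pools only sites with fewer than 5 subjects. A site of 5 has no deaths with probability 0.9⁵ = 59% at 10% mortality and 0.8⁵ = 33% at 20%. Such levels add nothing to the treatment estimate and can make the fit unstable.

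**The case against.** The strongest reply is that the adjusted analysis already exists. SAP 7.2.4 and Table 2 adjust for everything used in allocation. SAP 7.2 makes the secondary tests two-sided, so an excess of deaths is tested as well as a reduction. Both documents expect the Safety and ITT populations to be almost the same. A place late in the fixed sequence limits a confirmatory claim of benefit; it does not stop the odds ratio and interval from being reported and read for harm. All of this stands. A reader might infer from Protocol 11.9.2 that the trial has no adjusted comparison of deaths, or is materially less able to detect harm. The documents do not support that.

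The wording of 11.9.2 is also not clearly exhaustive. Protocol 11.9.4 uses almost the same phrase for blood pressure, and SAP 8.2 then adds anesthesia and alteplase to that model. This stands as a caution about reading the text as treatment and nothing else. But the SAP completed the blood pressure model and did not do the same for mortality.

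Deaths to Day 90 are also SAEs (Protocol 10.1) and so enter the SAE comparison. That comparison counts any serious event, so it does not isolate mortality.

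The reply does not answer two points. The existing adjusted analysis codes missing outcomes as deaths, and no text gives it the safety role. The first matters less if vital status is nearly complete: at 1.3% missing the planned model keeps part of the gain from adjustment.

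**Conclusion.** The point holds as a gap in specification with a modest cost in power. Neither planned analysis is an adjusted comparison of observed deaths, and the plan does not say which mortality odds ratio leads for safety.

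Allowing for simulation error, an adjusted observed-deaths model gains about 2 to 9 power points over the treatment-only model and about 2 to 12 over the missing-as-death model. These ranges rest on assumed mortality of 10-20%, a harm odds ratio of 1.5, moderate to strong covariates, and missingness unrelated to arm or outcome. Of the inputs, only the 1.3% and the 4% come from the documents, and both describe loss of outcome data in general; missing vital status may be rarer.

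A reader might also take adjustment to be free. It is not quite: with site in the model, sparse levels are a real difficulty. Severity is low to moderate.

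**What to change.** In Protocol 11.9.2 and SAP 8.0, specify one lead safety model for 90-day mortality:

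- Safety population, grouped by treatment received, using observed deaths only.
- Logistic regression with treatment, the alteplase-by-device strata, age, sex, baseline NIHSS, ASPECTS and occlusion location.
- Site replaced by the region grouping of SAP 6.5, or omitted, with the reason stated.
- Odds ratio and risk difference, each with a confidence interval, beside the crude counts and the number with unknown vital status in each arm.

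Add a sentence that the SAP 7.2.4 analysis serves the fixed efficacy sequence only. Two mortality odds ratios will still appear, but each will have a stated role.

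The cost is a short text change and one extra model. The covariates are already fixed at randomization, so no new data are needed. The downside is a covariate set slightly different from that of the efficacy model.

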6.1.4.1 Guidance on Definitions of Selected Safety Outcomes

Symptomatic intracranial hemorrhage (ICH) defined according to the Heidelberg classification, as a new ICH [intracerebral hemorrhage, SAH, intraventricular hemorrhage (IVH), subdural hematoma (SDH)] associated with clinical evidence of neurological worsening, in which, the hemorrhage is judged to be the most important cause of the neurological worsening. Clinical worsening will be guided by the NIHSS score of a minimum of two or more points different from baseline.

Major extracranial hemorrhage defined as life-threatening, resulting in hemodynamic compromise or hypovolemic shock, requiring inotropic support or other means to maintain cardiac output, requiring blood transfusion of more than two units of packed red blood cells, or associated with a fall in hemoglobin greater than or equal to 5 g/L.

Contrast media-induced nephropathy will be defined as a rise of the serum creatinine of ≥ 0.5 mg/dl (≥ 44 mmol/l) or a $\geq 25\%$ increase from baseline pre-treatment level within 3 days after the endovascular procedure without an alternative etiology. Any creatinine measurements conducted as part of the protocol or standard of care in the first 3 days after the endovascular procedure in patients suspected by their treating physician of having a contrast nephropathy will be considered for this adjudication. .

Total radiation dose will be measured in mSv and recorded directly from the CT scanner. Dose-length product will be recorded directly from the CT scanner.

Malignant MCA infarction will be defined as any large infarction with mass effect observed on imaging where treatment (medical or surgical) is required for the treatment of mass effect.

Hemicraniectomy will be defined as that surgical procedure used to decompress the swollen hemisphere.

Vessel perforation will be defined at angiography by the operator and associated with sub-arachnoid hemorrhage.

Iatrogenic arterial dissection will be defined at angiography by the operator.

Arterial access site hematoma will be assessed as a complication of arterial access puncture and defined by clinical examination and anatomic imaging.

Retroperitoneal hematoma will be assessed as a complication of groin puncture and defined by imaging (ultrasound or CTA or MR).

Femoral neuropathy will be defined clinically and shall be considered related to the procedure if it is ipsilateral to the angiography puncture site and occurring with several weeks of the procedure.

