8.3 Guidelines-based Medical/Stroke Unit Care

All acute stroke subjects should receive the best standard of care according to national guidelines. The model will be the Canadian best practices guidelines for acute stroke care. These are very

similar to the guidelines of the American Stroke Association and the European Stroke Organization. All subjects are expected to be admitted to hospital as part of routine standard of care.

It is expected that all subjects will undergo a routine work-up for the mechanism of their stroke and be treated appropriately and definitively. This is critically important because subjects who have an excellent early recovery are at the highest risk of early recurrent stroke.²⁴ We wish to prevent recurrent stroke from confounding the 30-day and 90-day clinical outcome such that subject who are well at discharge remain that way for the duration of the 90-day follow-up period.

We expect the following preventive care. Relevant subject with atrial fibrillation should be anti-coagulated. Patients with symptomatic carotid artery stenosis should undergo carotid revascularization early and definitely within two weeks of stroke onset.²⁵ Risk factors, including hypertension, elevated cholesterol, diabetes mellitus, tobacco smoking, should be treated appropriately and aggressively according to current standards of care.

We expect subjects to receive adequate hydration to prevent renal complications. Patients will receive intravenous radio-contrast media for CTA for endovascular intervention. While these medications are generally extremely safe in stroke patients,²⁶ simple hydration can prevent renal complications, particularly among patients with baseline borderline renal function and among those with diabetes mellitus. Further, patients with ischemic stroke are generally slightly hypovolemic at baseline. We recommend use of intravenous normal saline (0.9% saline) infusion at 1.5 – 2.0 cc/kg/h until the subject is eating and drinking safely and well. Therefore, for the typical subject this will mean intravenous normal saline at 75-125 cc/h overnight only. We do not recommend the use of bicarbonate solutions or N-acetyl-cysteine solutions for renal protection.^{27,28} In general, the risk of nephrotoxicity from modern non-ionic, iso-osmolar radiocontrast media is extremely low.

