10.6.2 Biochemistry and Hematology

Blood work will be taken at baseline and at 24 hours including: CBC (hemoglobin, platelets and hematocrit), electrolytes (sodium, potassium, chloride), INR, aPTT, serum creatinine and serum glucose. This is described in [Sections 8.6. , 8.11](#) and the Schedule of Assessments.

If the subject is female and is of childbearing potential, a pregnancy test (urine or serum point-of-care pregnancy test) must be completed. Clinically significant laboratory findings from the 24-hour sample (post dose) will be recorded on the e-CRF as AEs.

10.7 12-Lead Electrocardiogram Monitoring.

A 12-lead ECG will be performed at Baseline or, if the treating physician deems that an ECG will impede the subject's access to care, within 6 hours of randomization, and at approximately 24 Hours. Clinically significant findings on the 24-hour ECG will be recorded on the e-CRF as AEs.

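### A hemoglobin fall of only 5 g/L is enough on its own to class an extracranial bleed as major, far below the other criteria in the same definition; the threshold and its unit need confirming

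*Protocol*

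**What the plan says.** Protocol 6.1.4.1, Guidance on Definitions of Selected Safety Outcomes, opens the definition with severe states: "Major extracranial hemorrhage defined as life-threatening, resulting in hemodynamic compromise or hypovolemic shock, requiring inotropic support or other means to maintain cardiac output". It adds "requiring blood transfusion of more than two units of packed red blood cells" and ends with "or associated with a fall in hemoglobin greater than or equal to 5 g/L". The criteria are alternatives, so the last suffices alone once there is an extracranial hemorrhage. It has no time window, no rule for attributing the fall to the bleed, and no allowance for dilution.

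Three other places bear on it:

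- The same section defines access-site hematoma separately: "Arterial access site hematoma will be assessed as a complication of arterial access puncture and defined by clinical examination and anatomic imaging". Retroperitoneal hematoma also has its own entry. Neither entry says whether such a bleed can also count as major extracranial hemorrhage.
- Protocol 10.6.2 sets the scheduled measurements: "Blood work will be taken at baseline and at 24 hours including: CBC (hemoglobin, platelets and hematocrit". Section 8.11 puts the second sample at 24 ± 12 h.
- Protocol 8.3 calls for fluids in that interval: "We recommend use of intravenous normal saline (0.9% saline) infusion at 1.5 – 2.0 cc/kg/h". It then limits this: "for the typical subject this will mean intravenous normal saline at 75-125 cc/h overnight only".

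No other section of the protocol gives a different hemoglobin threshold. The SAP does not repeat the definition.

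**The concern.** A composite definition is only as strict as its weakest criterion. Here every criterion but the last describes a bleed that a clinician would call major unprompted. The last is met by a change so small that rehydration after a slightly dry baseline could account for some or all of it.

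Every subject is to have an arterial puncture and many will receive alteplase, so minor extracranial bleeds should be expected. If a share of them is moved into the major category by a 0.5 g/dL fall, the reported rate no longer describes serious bleeding. Any true difference between arms in serious bleeding is then harder to see.

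**Working it through.** The threshold is a stated definition, so there is no plan figure to reproduce. The check is one of units, of consistency within the sentence, and of scale.

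**1. Size of the threshold.** 5 g/L ÷ 10 = 0.5 g/dL. As a share of baseline hemoglobin (assumed values): 5/150 = 3.3%, 5/140 = 3.6%, 5/120 = 4.2%.

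**2. Against the transfusion criterion.** Assume that one unit of red cells corresponds to 7–10 g/L (not in the documents). Two units then correspond to 14–20 g/L, which is 14/5 = 2.8 to 20/5 = 4.0 times the hemoglobin criterion. The neighbouring criterion requires more than two units, so the hemoglobin criterion is at most about a quarter to a third as demanding.

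**3. Dilution.** Hemoglobin falls by 5 g/L when blood volume expands by b/(b − 5) − 1. For b = 140 g/L this is 140/135 − 1 = 3.7%; for b = 120 g/L it is 120/115 − 1 = 4.3%. The fluid in section 8.3, over an assumed 12 hours, is 75 × 12 = 900 mL to 125 × 12 = 1500 mL. How much stays in the circulation is not given, so this shows only that dilution could contribute materially.

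**4. Chance that a minor bleed is upgraded.** Take a subject who has a minor extracranial bleed that itself removes a negligible amount of hemoglobin. Let the change between samples be normal with mean fall m and SD s (both assumed, in g/L). Then P(fall ≥ 5) = 1 − Φ((5 − m)/s):

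| Mean fall m | s = 4 | s = 5 | s = 6 | s = 8 | s = 10 |
|---|---|---|---|---|---|
| 0 | 11% | 16% | 20% | 27% | 31% |
| 5 | 50% | 50% | 50% | 50% | 50% |
| 10 | 89% | 84% | 80% | 73% | 69% |

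These percentages are conditional on a bleed and are not shares of all subjects. The count mislabelled is (subjects) × (minor-bleed rate) × (this probability), and the documents give no minor-bleed rate. Per 100 such bleeds, 11–31 would be called major with no mean fall. For scale only, at 50 g/L (the same numeral in g/dL) the probability is at most 1 − Φ((50 − 10)/10) = 0.003% anywhere in the grid.

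**5. The adjacent unit.** The next definition has "a rise of the serum creatinine of ≥ 0.5 mg/dl (≥ 44 mmol/l". With creatinine at 113.12 g/mol, 0.5 mg/dL = 5 mg/L, and 5/113.12 = 0.0442 mmol/L = 44.2 µmol/L. The printed unit is wrong by a factor of 1000.

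**6. Effect on a comparison.** Suppose the true major-bleed rates are p1 and p0, and upgraded minor bleeds add the same c to each arm. The ratio becomes (p1 + c)/(p0 + c), which is nearer to 1 than p1/p0. The expected difference stays p1 − p0 but is estimated with more noise. This assumes that minor bleeding and fluids are alike in the two arms.

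**7. Where the label is used.** Protocol 6.1.4 names SAE frequency and 90-day mortality as the primary safety outcomes. SAP 8.1 tabulates events by MedDRA class and term, severity and relatedness. SAP Appendix 1 lists angioedema, hypotension and anaphylaxis terms as being of special interest, not bleeding. SAP 8.5 gives the data monitoring committee event codes, severity and relatedness. Seriousness follows its own criteria in Protocol 10.1. None of these depends on this definition.

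**The case against.** The strongest reply is that nothing planned turns on this label. The section is guidance, the outcome is not a primary safety outcome, and the SAP names no comparison that would be diluted. That stands, and it limits the point to classification and reporting.

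The reply also goes to the numbers. The fall must accompany an extracranial hemorrhage, so a reader who takes the table to mean that 11% or more of all subjects would be counted as major bleeds would be wrong. A subject who never bled has nothing to classify. Nor do the documents support saying that most small hematomas become major. In the table that requires an assumed mean fall above 5 g/L, and both the means and the SDs are assumptions. The fluid recommendation is limited to overnight in the typical subject, in patients described as slightly hypovolemic, so the amount of dilution is uncertain. All of this stands.

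Access-site hematoma has its own entry, and the protocol does not direct that it also be counted as major. It does not exclude it either, so the overlap is left open.

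Finally, a reader might infer that 5 g/dL was intended. The creatinine error shows that units in this section were not checked reliably. It does not show what the hemoglobin figure should be.

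None of this answers the central point: as written, 0.5 g/dL stands as an equal alternative to shock and to transfusion of more than two units, and nothing elsewhere corrects it.

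**Conclusion.** The definition does not hold together. The hemoglobin criterion is 0.5 g/dL, some 3.3–4.2% of an assumed baseline of 150–120 g/L. It is a quarter to a third of what two transfused units would represent at an assumed 7–10 g/L per unit. A minor extracranial bleed with a small fall therefore meets the definition of major.

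The consequence is inflated counts of this one outcome and a weaker contrast between arms in serious bleeding if it is reported. How many events are affected cannot be stated, because the documents give neither a minor-bleed rate nor the distribution of the hemoglobin change. The primary efficacy analysis, the primary safety outcomes and the SAP's named safety tables are untouched. Whether the fault is the number or the unit is for the sponsor to say.

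**What to change.** - Confirm the intended hemoglobin threshold and unit, and print it in both g/L and g/dL.
- Reconcile it with the criterion of more than two transfused units, so that the alternatives describe comparable severity. If 5 g/L is confirmed as intended, say why, so that readers do not take the label to mean serious bleeding.
- Correct the creatinine unit in the contrast-nephropathy definition to µmol/L.
- If the threshold changes, reclassify recorded extracranial bleeds where hemoglobin values exist. Scheduled values exist only at baseline and 24 ± 12 h; bleeds after that need local laboratory results, so complete re-derivation cannot be promised.

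The cost is a short protocol correction and a small amount of re-derivation. If the threshold is raised, fewer events will be labelled major.
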